**Blinded Phase of Study**

Encounter 6 – Office Visit [first time at ISMMS]: Confirmation of eligibility, randomization and device and diary training Visit. Subjects deemed eligible for study participation up to this point, will be invited to ISMMS in the Annenberg Building located at [name], within one week after Visit 5. They will sign consent for study participation. They will provide a fifth rating of widespread pain severity over the past 24 hours at this encounter on a 10-point VAS. The fifth pain rating will be added to the 4 VAS pain ratings done in the week after intake at the VA. If the median of all 5 VAS widespread pain ratings remains at least a 5, subjects remain eligible to participate. Then medical and eligibility information obtained on Encounters #1 through 5 will be briefly reviewed, a pregnancy test will be administered, and a medication history will be taken. If still deemed eligible to continue on in the study, they then complete questionnaires [MIDAS, SF-36 and HADS] and undergo a brief baseline medical evaluation consisting a physical examination including vital signs and a tender point examination and of asking the veteran questions to determine if s/he fulfill criteria for chronic fatigue syndrome, fibromyalgia, and/or irritable bowel syndrome and for Gulf War Illness. Subjects are then randomized and trained by the blinded trainer to use the device to which they have been assigned [devices are received with serial numbers covered and numbered sequentially so the trainer is blinded to condition]. Subjects will receive identical instruction and guidelines regardless of which device they receive. To be sure the subject knows how to use the device; s/he will be given a quiz about using the device after training. They will also be trained on use of a daily diary (paper and electronic) to be completed after each of the three daily treatments. Subjects will be given an unique 10 digit identifier that they will used to log into the Merge IBM site, in which they will be prompted to create a username and password.

Veterans will be reminded [as specified in the study consent form] that in order to proceed to the open label phase of the study, they must administer at least 70% of all programmed stimuli as well as complete at least 70% of the diary entries; however, because the device needs to be sent back to the

	Protocol Name:	Vagus Nerve Stimulation: A Non-Invasive Treatment to Improve the health of Gulf Veterans with Gulf War Illness
	Principal Investigator:	[name]
	Primary Contact Name/Contact Info:	[name]: [contact]
	Date Revised:	07/15/2019
	Study Number:	HSM# 16-00097

manufacturer in order to obtain the stimulation data, resulting in a 3-4 day delay in retrieving the data, we will not be able to use this criterion to advance subjects to get an actual unit in the open label phase of the study. Therefore, although we will tell subjects they have to deliver at least 70% of all programmed stimuli in order to get an active unit, the only criterion that will be enforced is that they will have had to complete 70% of diary entries, which will be verified by reviewing their diary logs at Encounter #14. This procedure is in place so that veterans who do not perceive benefit from the treatment [i.e. those receiving sham stimulation] will continue to treat themselves per protocol; this is critical for the overall purpose of the study in order to be able to infer that it was the active treatment that produced the therapeutic effect. If subjects did not continue stimulating themselves, we would be unable to determine whether a placebo effect existed or not.

Encounter 7 – Phone Call: Within 7 ( $\pm 4$ ) days after Encounter 6 (Day 0), subject will receive a phone call from study personnel to inquire about any negative effects of stimulation (Adverse Events, AEs) and to check if they are using the diary after each stimulation.

Encounter 8 – Phone Call: Within 23 ( $\pm 4$ ) days after Encounter 6 (Day 0), subject will receive phone call from study personnel to inquire about AEs, check as to use of diary, rating of widespread pain over past 24 hours on a 10-point VAS, and potential desire to reduce medications.

Encounter 9 – Phone Call: Within 46 ( $\pm 4$ ) days after Encounter 6 (Day 0) subject will receive phone call from study personnel to inquire about AEs, check as to use of diary, rating of widespread pain over past 24 hours on a 10-point VAS, and potential desire to reduce medications.

Encounter 10 – Phone Call: Within 63 ( $\pm 4$ ) days after Encounter 6 (Day 0) subject will receive phone call from study personnel to inquire about AEs, check as to use of diary, rating of widespread pain over past 24 hours on a 10-point VAS, and potential desire to reduce medications.

Encounter 11 – Phone Call: Within 65 ( $\pm 4$ ) days after Encounter 6 (Day 0) subject will receive phone call from study personnel to rate their widespread pain over past 24 hours on a 10-point VAS. .

Encounter 12 – Phone Call: Within 67 ( $\pm 4$ ) days after Encounter 6 (Day 0) subject will receive phone call from study personnel to rate their widespread pain over past 24 hours on a 10-point VAS.

Encounter 13 – Phone Call: Within 69 ( $\pm 4$ ) days after Encounter 6 (Day 0) subject will receive phone call from study personnel to rate their widespread pain over past 24 hours on a 10-point VAS.

Encounter 14 – Office Visit: Within 70 ( $\pm 4$ ) days after Encounter 6 (Day 0) subject will come to ISMMS. They will provide the 5th pain rating to arrive at the median pain rating. They will fill out same questionnaires they filled out on study Encounter 6 as well as the patient global measure of change and the measure of certainty, and will provide information about AEs and medication changes. They will again have the same brief medical evaluation as was done on Encounter #6 to provide data as to whether they fulfill criteria for GWI, CFS, IBS, MCS or FM. They will exit the blinded part of the study and return their original unit. Subjects who have completed at least 70% of diary entries will be given the active unit and will be trained on it again. They will be given new paper diaries and sent home. They will continue to use their electronic diary logon information to access their diary.

	Protocol Name:	Vagus Nerve Stimulation: A Non-Invasive Treatment to Improve the health of Gulf Veterans with Gulf War Illness
	Principal Investigator:	[name]
	Primary Contact Name/Contact Info:	[name]: [contact]
	Date Revised:	07/15/2019
	Study Number:	HSM# 16-00097

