**b) Inclusion and Exclusion Criteria**

**Inclusion Criteria**

To be eligible for enrollment in the Study, patients must meet all of the following criteria:

1. Patient is a veteran of the 1990-91 Gulf War, aged at least 42 years old.
2. Patient fulfills Kansas criteria for Gulf War Illness including endorsement of musculoskeletal pain at moderate or severe intensities. This means patient has to endorse symptoms in at least 2 more of the following problem areas: Fatigue/sleep; cognitive and mood; Gastrointestinal; respiratory; skin.
3. Patient has widespread chronic pain as evidenced by endorsement of pain in at least 3 bodily quadrants plus in the axial skeleton.
4. Patient has a median 24 hour widespread pain score of at least 5 on a 0 to 10 VAS.
5. To be considered having migraine, the patient must fulfill IHS criteria.
6. Patient agrees to use the study device as intended, follow all of the requirements of the study including completion of diary after each self-treatment, follow-up visit requirements, complete self

	Protocol Name:	Vagus Nerve Stimulation: A Non-Invasive Treatment to Improve the health of Gulf Veterans with Gulf War Illness
	Principal Investigator:	[name]
	Primary Contact Name/Contact Info:	[name]: [contact]
	Date Revised:	07/15/2019
	Study Number:	HSM# 16-00097

assessment questionnaires as scheduled, and report any adverse device effects to the study center within 24 hours of such adverse device effect.

7. Patient is able to provide written Informed Consent.

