**Open Label Phase of Study**

Encounter 15 – Phone Call: Within 77 ( $\pm 4$ ) days after Encounter 6 (Day 0), subject will receive phone call from study personnel to inquire about any negative effects of stimulation (Adverse Events, AEs) and to check about use of diary..

Encounter 16 – Phone Call: Within 93 ( $\pm 4$ ) days after Encounter 6 (Day 0), subject will receive a phone call from study personnel to inquire about AEs, check as to use of diary, rating of widespread pain over past 24 hours on a 10-point VAS, and potential desire to reduce medications.

Encounter 17 – Phone Call: Within 116 ( $\pm 4$ ) days after Encounter 6 (Day 0) subject will receive phone call from study personnel to inquire about AEs, check as to use of diary, rating of widespread pain over past 24 hours on a 10-point VAS, and potential desire to reduce medications.

Encounter 18 – Phone Call: Within 133 ( $\pm 4$ ) days after Encounter 6 (Day 0) subject will receive phone call from study personnel to inquire about AEs, check as to use of diary, rating of widespread pain over past 24 hours on a 10-point VAS, and potential desire to reduce medications.

Encounter 19 – Phone Call: Within 135 ( $\pm 4$ ) days after Encounter 6 (Day 0) subject will receive phone call from study personnel to rate their widespread pain over past 24 hours on a 10-point VAS.

Encounter 20 – Phone Call: Within 137 ( $\pm 4$ ) days after Encounter 6 (Day 0) subject will receive phone call from study personnel to rate their widespread pain over past 24 hours on a 10-point VAS.

Encounter 21 – Phone Call: Within 139 ( $\pm 4$ ) days after Encounter 6 (Day 0) subject will receive phone call from study personnel to rate their widespread pain over past 24 hours on a 10-point VAS.

Encounter 22 – Office Visit: Within 140 ( $\pm 4$ ) days after Encounter 6 (Day 0) subject will come to ISMMS. They will provide the 5th pain rating to arrive at the median pain rating; they will fill out the same questionnaires they filled out on Encounter 14 [except for Measure of Certainty], provide information about AEs, indicate any medication changes. They will again have the same brief medical evaluation as was done on Encounter #6.

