**Name: [name]: Independent Clinical Data/Study Monitor**

**Mailing Address: M Squared Associates; [name]**

**[contact]**

**Email: [[contact]](mailto:[contact])**

2. The hand held, patient controlled, transcutaneous nVNS device presents minimal risk to the user. That interpretation can be made from the fact that the device has been now used with hundreds of research subjects and by thousands of patients in Europe and Australia (where it has been approved for sale) with minimal side effects. There has never been a serious adverse effect attributed to its use.
3. The specific items that will be monitored for safety include adverse events, subject's compliance with the protocol, and drop outs.
4. Since no clinical trial using nVNS has ever had to be halted, we doubt this will happen herein but should it happen that information will be passed onto appropriate DOD personnel monitoring the Human Studies regulatory issues related to this trial.
5. Data accuracy and completeness: The data collection tool for this trial will be a validated electronic data capture (EDC) system using eCRFs. Subject data necessary for analysis and reporting will be entered into a validated database or data system using source documentation

	Protocol Name:	Vagus Nerve Stimulation: A Non-Invasive Treatment to Improve the health of Gulf Veterans with Gulf War Illness
	Principal Investigator:	[name]
	Primary Contact Name/Contact Info:	[name]: [contact]
	Date Revised:	07/15/2019
	Study Number:	HSM# 16-00097

available at the site. The PI is to maintain all source documents as required by the protocol, including laboratory results, Subject Case Report Forms, supporting medical records, documentation of all study visits and telephone calls and Informed Consents. The source documents will be used at monitoring visits to verify information submitted on the Subject Case Report Forms.

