5. Duties of the Independent Medical Monitor: Both the study PI, [name], and the Independent Medical Monitor, [name], will review any unanticipated problems involving risk to subjects or others, serious adverse events and all subject deaths associated with the protocol and provide an unbiased written report of the event. [name] will transmit information concerning such an event to the IRB with his input as to whether the event was related to the study device; this material will also be given to [name] to allow her to comment on whether she concurs with the details of [name] report. Reports for events determined by either [name] or [name] to be possibly or definitely related to participation and reports of events resulting in death will be promptly forwarded to the FDA, to the device manufacturer, electroCore, and to USAMRMC ORP HRPO. The independent Medical Monitor has the authority to stop the research protocol in progress, remove individual human subjects from the research protocol, and take whatever steps are necessary to protect the safety and well-being of human subjects until the IRB assesses the Independent Medical Monitor's report. [name] and [name] will meet biannually.

7. Duties of the Independent Clinical Study Monitor: The Clinical Study Monitor will assure that complete, accurate and timely data are submitted, that protocol requirements are followed, and that the safety and rights of subjects is being protected. This will include on-site checking of the eCRF for completeness and clarity, crosschecking with source documents, and clarification of administrative matters as follows:

- Ongoing compliance with the study protocol.
- Ongoing compliance with any conditions of approval of the reviewing IRB and the IDE regulations.
- Maintenance of complete and accurate study records including quality control checks on CRFs
- Continued acceptability of the site’s facilities.

All monitoring tasks will be carried out in such a manner as to protect patient confidentiality and protected health information. Data problems will be addressed in contacts with the study staff. [name] will meet with [name] on a quarterly basis.

8. If a temporary or permanent suspension of this study should occur, in addition to the PPHS, [name] will report this immediately to DoD and to electroCore LLC.

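### AEs are explained only as effects of stimulation and the 24-hour report covers only device effects, so non-serious events that a patient does not blame on the device may go unrecorded

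*Combined protocol and SAP*

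**What the plan says.** Section 5 f) has staff collect AEs at ten contacts. At Encounter 7, where the abbreviation is introduced, the call is made "to inquire about any negative effects of stimulation (Adverse Events, AEs". Encounter 15, the first call of the open-label phase, has the same purpose: "to inquire about any negative effects of stimulation (Adverse Events, AEs) and to check about use of diary".

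The other eight contacts use the bare abbreviation. At Encounters 8 to 10 the "subject will receive phone call from study personnel to inquire about AEs, check as to use of diary", and Encounters 16 to 18 are alike. At Encounter 14 subjects "will provide information about AEs and medication changes"; at Encounter 22 they "provide information about AEs, indicate any medication changes".

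Under inclusion criterion 6 in section 5 b), the patient agrees to "report any adverse device effects to the study center within 24 hours of such adverse device effect".

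The safety monitoring plan in section 5 i) is broader: "The specific items that will be monitored for safety include adverse events, subject's compliance with the protocol, and drop outs". It has the PI and the Independent Medical Monitor review unanticipated problems, serious adverse events and deaths. The PI reports to the IRB "with his input as to whether the event was related to the study device", and the monitor comments on that report.

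**The concern.** Relatedness is a judgement for the PI and the medical monitor, but they can judge only what reaches them. If the patient is asked about effects of stimulation, a symptom that the patient puts down to something else can be left out before anyone qualified has considered it.

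That is a practical risk in this population. Section 6 (Risks to Subjects) names headache or migraine, dizziness, shortness of breath, irregular heart beat and gastrointestinal discomfort. The Kansas criteria in inclusion criterion 2 include gastrointestinal and respiratory domains, and the Background cites migraine in 64% of Gulf veterans with GWI. A new or worse symptom is easily read as more of the same illness.

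Perceived assignment may add to this in the blinded phase, because a patient who believes the unit is sham has less reason to call anything an effect of stimulation. At stake are the completeness of the non-serious AE record and the use of the sham arm as a background rate. Adverse events are a listed endpoint, and section 5 d) says the results will support a proposal for a multi-site trial aimed at FDA approval.

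**Working it through.** No stated figure is in question, so the check is of the text.

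1. **Count of AE contacts by wording (section 5 f).**

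| Phase | Causal wording | Bare abbreviation | Total |
|---|---|---|---|
| Blinded | Encounter 7 | Encounters 8, 9, 10, 14 | 5 |
| Open label | Encounter 15 | Encounters 16, 17, 18, 22 | 5 |
| Both | 2 | 8 | 10 |

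2. **Meaning carried by the bare abbreviation.** The parenthesis at Encounter 7, repeated at Encounter 15, is the only explanation of the abbreviation in the supplied text. No cause-neutral definition, non-leading question or AE form appears. The eight bare uses can therefore be read as carrying the same meaning.

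3. **Routes other than the AE inquiry.**
 - The criterion 6 report is limited to device effects.
 - The diary asks treatment time, intensity and whether there was a headache of at least 4 hours. It captures such headaches without asking about cause; it has no item for shorter headaches or any other symptom.
 - The medical evaluation repeated at Encounters 14 and 22 includes a physical examination and vital signs, and serves to classify GWI and related syndromes. It would not reliably recover a symptom that came and went between visits. The only ECG described is at Encounter 1.
 - Medication questions are indirect.
 - In the blinded phase the longest gap between AE inquiries is Encounter 8 to 9: 46 − 23 = 23 days, or (46 + 4) − (23 − 4) = 31 days at the edges of the windows. This bears on recall and is not itself evidence of an attribution filter.

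4. **The protocol's own precedent.** The Background reports, as an adverse reaction in the implanted-device study, severe dyspepsia that was thought not to be device-related. A patient asked only about effects of stimulation might not have mentioned it.

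5. **What unequal attribution would do (all reporting shares and event risks assumed; none is in the documents).** Take 20 patients per arm, the same true risk p in both, and reported shares a (active) and s (sham). The recorded risk ratio is (p × a)/(p × s) = a/s, so p cancels. With p = 0.40 the true count is 40 × 0.40 = 16 events.

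| a | s | Recorded, active | Recorded, sham | Ratio | Missed of 16 |
|---|---|---|---|---|---|
| 0.9 | 0.9 | 20 × 0.40 × 0.9 = 7.2 | 7.2 | 1.00 | 1.6 |
| 0.9 | 0.7 | 7.2 | 20 × 0.40 × 0.7 = 5.6 | 1.29 | 3.2 |
| 0.9 | 0.5 | 7.2 | 20 × 0.40 × 0.5 = 4.0 | 1.80 | 4.8 |

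The table shows the direction and the dependence on assumptions. With equal shares events are lost but the ratio is undistorted.

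**The case against.** The strongest reply is that the text does not make the patient's opinion the recording rule. Eight of ten contacts carry no causal wording, and all ten sentences state what a contact is for, not what staff say. Section 5 e) and the monitoring plan name adverse events with no causal limit, and section 5 h) draws safety data from every subject who used either apparatus. Serious events and deaths, once known, are reviewed whatever the patient thinks. Criterion 6 is an agreement about rapid reporting on top of the scheduled contacts, and participants have the investigators' phone numbers. The eCRFs sit in the IDE application and staff also read a separate Investigational Plan; neither was available, and either may hold a neutral definition or form.

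Most of this stands and sets the limits of the point. It confines the concern to non-serious events, takes headaches of at least 4 hours out of it, and makes it a possibility. It does not supply a cause-neutral meaning for AEs.

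A reader might go further and infer that the patient's guess at treatment arm decides which events are recorded, or that the sham comparison will show a false excess of some definite size. The documents support neither. Nothing ties the guess to AE recording, and the guess can matter only before Encounter 14, since every continuing subject then has an active unit. Nor do they say that the sham unit produces no sensation. No between-arm AE test is stated (the Fisher test in section 5 h) is for drop-out), so any imbalance would affect descriptive tabulation.

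**Conclusion.** The point holds in a limited form. The only explanation given for AEs builds in attribution to stimulation, and the rapid report is limited to device effects. Followed as written, non-serious events that the patient does not blame on the device may be missed, and in the blinded phase possibly unequally by perceived arm. The size is unknown, and the illustrative ratios of 1.00 to 1.80 follow entirely from the assumed reporting shares.

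The conclusion rests on two assumptions: that staff follow the protocol wording, and that no unseen document overrides it. The efficacy analyses are not affected. The change is worth making because it is cheap and improves ascertainment, not because bias has been shown.

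**What to change.** At Encounters 7-10, 14-18 and 22, replace the causal phrase or bare abbreviation with one neutral open question: has there been any new or worsened medical problem since the last contact, whether or not the patient thinks the device caused it? Leave relatedness to the PI and the Independent Medical Monitor, as section 5 i) already provides.

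State in section 5 b) or 5 f) that the criterion 6 report of device effects is additional to this inquiry and does not define which AEs are recorded. There is no need to widen the 24-hour report to every new or worsened event: in a fluctuating multi-symptom illness the burden is debatable, and the scheduled question meets the need.

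Check the eCRFs and the Investigational Plan first. If they are already neutral, the change is only to align the protocol text with them.

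The cost is protocol and call-guide wording, with no added visits. The downside is more unrelated events to record and assess in about 40 patients.

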**Open Label Phase of Study**

Encounter 15 – Phone Call: Within 77 ( $\pm 4$ ) days after Encounter 6 (Day 0), subject will receive phone call from study personnel to inquire about any negative effects of stimulation (Adverse Events, AEs) and to check about use of diary..

Encounter 16 – Phone Call: Within 93 ( $\pm 4$ ) days after Encounter 6 (Day 0), subject will receive a phone call from study personnel to inquire about AEs, check as to use of diary, rating of widespread pain over past 24 hours on a 10-point VAS, and potential desire to reduce medications.

Encounter 17 – Phone Call: Within 116 ( $\pm 4$ ) days after Encounter 6 (Day 0) subject will receive phone call from study personnel to inquire about AEs, check as to use of diary, rating of widespread pain over past 24 hours on a 10-point VAS, and potential desire to reduce medications.

Encounter 18 – Phone Call: Within 133 ( $\pm 4$ ) days after Encounter 6 (Day 0) subject will receive phone call from study personnel to inquire about AEs, check as to use of diary, rating of widespread pain over past 24 hours on a 10-point VAS, and potential desire to reduce medications.

Encounter 19 – Phone Call: Within 135 ( $\pm 4$ ) days after Encounter 6 (Day 0) subject will receive phone call from study personnel to rate their widespread pain over past 24 hours on a 10-point VAS.

Encounter 20 – Phone Call: Within 137 ( $\pm 4$ ) days after Encounter 6 (Day 0) subject will receive phone call from study personnel to rate their widespread pain over past 24 hours on a 10-point VAS.

Encounter 21 – Phone Call: Within 139 ( $\pm 4$ ) days after Encounter 6 (Day 0) subject will receive phone call from study personnel to rate their widespread pain over past 24 hours on a 10-point VAS.

Encounter 22 – Office Visit: Within 140 ( $\pm 4$ ) days after Encounter 6 (Day 0) subject will come to ISMMS. They will provide the 5th pain rating to arrive at the median pain rating; they will fill out the same questionnaires they filled out on Encounter 14 [except for Measure of Certainty], provide information about AEs, indicate any medication changes. They will again have the same brief medical evaluation as was done on Encounter #6.

During this visit, the subject will be informed that although the requirement to deliver at least 70% of the programmed stimulus was to be checked at Visit #14, along with completion of at least 70% of the diary entries, the device criterion was not actually enforced at that time because the data were not available until analyzed by the manufacturer. Subjects will be explained that this deception was in place in order to ensure that they continued to use the device as instructed, regardless of whether they thought they had a sham or active unit, allowing us to assess whether a positive effect of their using the actual device was related to its stimulating the vagus or was simply a placebo response. They will also be informed that even if the device data were to indicate that they did not meet the minimum 70% use requirement, it would not have affected their eligibility to participate in or complete the open label phase of the study.

	Protocol Name:	Vagus Nerve Stimulation: A Non-Invasive Treatment to Improve the health of Gulf Veterans with Gulf War Illness
	Principal Investigator:	[name]
	Primary Contact Name/Contact Info:	[name]: [contact]
	Date Revised:	07/15/2019
	Study Number:	HSM# 16-00097

